6.2 Secondary Objectives

- i. To assess clinical tolerability of inhaled R848 with regards to FEV₁
- ii. To assess clinical tolerability of inhaled R848 with regards to physiological observations (temperature, pulse, blood pressure)
- iii. To assess change in peripheral eosinophil and lymphocyte counts after inhaled R848
- iv. To assess change in serum CRP after inhaled R848

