7. STUDY DESIGN

7.1 Summary of Trial Design

Nasal administration of R848 has been shown to cause dose-dependent (10 to 100 µg/mL) induction of mucosal innate immune responses (11, 12). The current study will aim to nebulise R848 into the lower airways using a similar dosing regimen and using a nebulisation technique well established using inhaled lipopolysaccharide (LPS) challenge (15). The design of the study is broadly based on a previously published clinical trial of an inhaled TLR7 agonist (10).

Single ascending dose (0.1, 1, 10, 100 µg/mL) nebulisation of R848 will be performed in healthy volunteers (up to n = 24) and subsequently in volunteers with asthma (n = 6).

All volunteers will receive only a single dose and the starting dose cohort for nebulised challenge will be 100-fold lower than the dose administered in the nose to ensure clinical tolerability.

For each dose-cohort (n = 6), participants will be randomised to either R848 (n = 4) or saline (n = 2).

A summary of the study design is outlined in [Appendix A](#).

The study will start with a small “sample only” cohort of six participants without asthma who will be recruited for the collection of nasal brush, sputum, and blood samples to optimise sample processing protocols prior to the main study.

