7.3 Secondary Outcome Measures

- i. Change in FEV₁ after 1, 4, 8, 24 and 48 hours of single ascending dose inhaled R848
- ii. Change in physiological observations (temperature, pulse rate and blood pressure) after 1, 4, 8, 24 and 48 hours of single ascending dose inhaled R848
- iii. Change in peripheral eosinophil and lymphocyte counts after 4, 24 and 48 hours of single ascending dose inhaled R848
- iv. Change in serum CRP after 4, 24 and 48 hours of single ascending dose inhaled R848

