9.1.4 Induced sputum

This will be performed using hypertonic saline at the screening visit and 24 hours after intervention using standardised techniques (16) over a 15-20 minute period to obtain sputum that can be analysed for CXCL10 levels. Salbutamol will be co-administered as a bronchodilator to reduce the chances of bronchoconstriction.

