9.4.1 Visit 1 (Day 1)

This will take place over 24 hours including an overnight stay in the CCRC. Baseline assessments will include:

- Spirometry
- Physiological observations (temperature, pulse, and blood pressure)
- Nasosorption - to determine baseline nasal immune profile
- Blood tests (FBC, CRP, Serum)

Volunteers will have been randomised to receive either R848 or saline via a breath-actuated nebuliser ([Aeroeclipse II](#)). After administration, they will be monitored at regular intervals by the clinical research team to check for clinical tolerability and repeat blood tests. The following morning after 24 hours, volunteers will subsequently have repeat blood tests as well as a repeat induced sputum performed.

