10.2 Dose Escalation

The following doses of nebulised R848 will be tested using a single dose escalation design: 0.1, 1, 10, 100 µg/mL. Six volunteers will be involved in each dose cohort with only a single dose given to each participant.

Each participant will be administered a dose of R848 or saline in a volume of approximately 1 mL (optimal volume to be confirmed after testing) using a breath-actuated nebuliser.

At the end of each dose cohort, CXCL10 levels in sputum and blood will be assessed and compared between saline and R848. If there are no statistically significant differences

between groups, and the dose is tolerable for volunteers, then the study will proceed to the next dose cohort.

Spirometry will be monitored regularly after inhaled challenge. Bronchodilator drugs will be available on standby for administration if volunteers have symptoms of breathlessness or tight chest associated with a significant drop in FEV₁ ($\geq 20\%$) from baseline.

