12. STATISTICS

12.1 *Description of Statistical Methods*

CXCL10 will be measured in sputum and serum 24 hours after each ascending dose of inhaled R848 (n = 4) and compared to inhaled saline (n = 2). CXCL10 levels will be compared between groups using unpaired t-tests.

Spirometry (FEV₁), physiological assessments (temperature, pulse, blood pressure) and leukocyte differential counts from FBC samples measured after challenge will be compared to baseline values using one-way analysis of variance (ANOVA).

12.2 *The Number of Participants*

Nasal R848 is a suitable method of inducing nasal innate immune responses (evidenced by a rise in interferon levels) in healthy individuals and those with asthma (11, 12). Therefore, it is anticipated that inhaled R848 will have a similar effect in inducing lung and peripheral innate immune responses even in a small number of participants.

The number of participants in each dose cohort of the dose finding phase of the study (n = 4 R848, n = 2 saline) is based on AstraZeneca's clinical trial of their inhaled TLR7 agonist (a compound with similar effects) (10), and was a suitable number of participants for assessing innate immune responses as evidenced by a rise in CXCL10 in sputum and serum.

12.3 *The Level of Statistical Significance*

A P-value of < 0.05 will be taken to indicate statistical significance.

12.4 *Procedure for Accounting for Missing, Unused, and Spurious Data.*

Missing clinical data points will be imputed as the mean of values from that volunteer.

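### Section 12.1 tests FEV1, observations and leukocyte counts only against baseline by an unspecified one-way ANOVA, names no R848-saline comparison for them, and gives CRP no analysis

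*Combined protocol and SAP*

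**What the plan says.** Section 12.1 contains two analysis sentences. The first compares CXCL10 between R848 and saline by unpaired t-tests. The second covers FEV1, temperature, pulse, blood pressure and leukocyte differential counts, which, "measured after challenge will be compared to baseline values using one-way analysis of variance (ANOVA"). It does not say repeated-measures. It does not say whether R848 volunteers, saline volunteers or both enter, or whether doses are analysed separately.

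The design provides a control: in each cohort "participants will be randomised to either R848 (n = 4) or saline (n = 2"). Outside section 12, the only planned comparison of arms is in section 10.2, and it concerns the biomarker: "CXCL10 levels in sputum and blood will be assessed and compared between saline and R848".

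Section 7.3 lists FEV1 and observations at 1, 4, 8, 24 and 48 h, and eosinophils, lymphocytes and CRP at 4, 24 and 48 h. With baseline, each volunteer therefore contributes six or four values.

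CRP is a secondary objective (section 6.2: "To assess change in serum CRP after inhaled R848") and a secondary outcome (section 7.3: "Change in serum CRP after 4, 24 and 48 hours of single ascending dose inhaled R848"). Section 9.1.3 schedules the blood for it. Section 12 does not mention it: the bracket after physiological assessments lists only temperature, pulse and blood pressure, and CRP is not a leukocyte count.

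**The concern.** FEV1 and the observations carry the tolerability objectives; section 6.2 includes "To assess clinical tolerability of inhaled R848 with regards to physiological observations (temperature, pulse, blood pressure"). Counts and CRP are objectives in their own right. A change from baseline after inhaling R848 has several possible causes: the drug, the time of day, the nebulisation, or the study procedures. The saline volunteers follow the same schedule, so the difference between arms is what isolates the drug. Without that comparison, a reported group change cannot be attributed to R848, and an absence of change is hard to interpret.

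The sputum procedure may add to this at 24 h. Section 9.1.4 states: "Salbutamol will be co-administered as a bronchodilator to reduce the chances of bronchoconstriction". Section 9.4.1 says that after 24 hours "volunteers will subsequently have repeat blood tests as well as a repeat induced sputum performed". This matters only if induction comes before the 24 h spirometry and observations, and the order is not stated. It cannot affect 1, 4 or 8 h.

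What is at stake is the reported group-level result. Adverse event recording (section 11.5) and individual FEV1 monitoring (section 10.2) do not use this test, and section 10.2 does not tie its escalation judgement to it.

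**Working it through.** **No figure to reproduce.** The plan gives no SD, effect size or power for these outcomes. All SDs and effects below are assumptions, with ranges. The level is 0.05 (section 12.3), the cohort is 4 v 2 (section 7.1), and there are six times (0, 1, 4, 8, 24, 48 h; section 7.3). Errors are normal with a constant within-person SD *w* and between-person SD *b*.

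**1. Repeated-measures reading, no drug effect (temperature).** Assumed daytime curve: rise × (0, 0.25, 0.75, 1, 0, 0), with rise 0.2-0.4 °C, *b* = 0.25 °C and *w* = 0.15-0.30 °C. The sum of squared deviations of the pattern from its mean is 1.625 − 2²/6 = 0.958. The within-subject F has noncentrality λ = n × 0.958 × rise² / w².

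| Analysed | λ, low to high | df | Significant |
|---|---|---|---|
| 4 R848 | 4×0.958×0.04/0.09 = 1.7 to 4×0.958×0.16/0.0225 = 27.3 | 5, 15 | 11-94% |
| All 6 | 2.6 to 40.9 | 5, 25 | 16-99.8% |
| Group × time, 4 v 2 | 0 (both arms share the curve) | 5, 20 | about 5% |

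**2. Independent-groups reading (FEV1).** Assumed *b* = 0.5-0.7 L and *w* = 0.10-0.20 L; mean fall × (0, 1, 0.5, 0, 0, 0). Under this reading the error term estimates b² + w². At *b* = 0.6 and *w* = 0.15 that is 0.36 + 0.0225 = 0.3825, against 0.0225 within person: 17 times larger. Simulated detection (40,000 runs per setting):

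| Analysed | Mean fall | Independent groups | Repeated measures |
|---|---|---|---|
| 4 R848 | 0.7 L | about 12-30% | over 99% |
| 4 R848 | 0.35 L | 1-4% | 54-99% |
| All 6 (4 with the fall, 2 without) | 0.7 L | 2-7% | 86-100% |

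With no change at all, the independent-groups test at n = 4 rejects in 0.1% of runs or fewer, not 5%.

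**3. What the saline contrast can detect (FEV1, group × time).** The pattern's sum of squares is 1.25 − 1.5²/6 = 0.875, and λ = [n₁n₂/(n₁+n₂)] × 0.875 × fall² / w².

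| Arms | 0.7 L | 0.35 L |
|---|---|---|
| 4 v 2 (df 5, 20) | 72-100% | 21-72% |
| 4 v 8 pooled saline (df 5, 50) | 99-100% | 46-99% |

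For example, 4 v 2 with a 0.7 L fall and *w* = 0.20 gives λ = (8/6) × 0.875 × 0.49/0.04 = 14.3.

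**4. Precision of the contrast at one time.** The half-width of the 95% interval for the difference in change is t × w × √2 × √(1/n₁ + 1/n₂).

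- 4 v 2, change score (4 df): 2.776 × 0.10 × 1.414 × 0.866 = 0.34 L, up to 0.68 L at *w* = 0.20.
- 4 v 2, random-intercept model (20 df, t = 2.086): 0.26-0.51 L.
- 4 v 8, change score (10 df, t = 2.228; √(1/4 + 1/8) = 0.612): 0.19-0.39 L.
- 4 v 8, random-intercept model (50 df, t = 2.009): 0.17-0.35 L.

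**5. Number of contrasts per dose.** Four outcomes × 5 times (FEV1, temperature, pulse, blood pressure counted once) plus three outcomes × 3 times (eosinophils, lymphocytes, CRP) gives 20 + 9 = 29. With no effect, 29 × 0.05 = 1.45 intervals would exclude zero by chance.

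**The case against.** The outcomes are worded as changes and the comparison is with baseline values, so within-person analysis is the likelier intention; one added word would settle that. This stands. The independent-groups figures show the cost of the ambiguity and are not the main point. The missing comparison with saline remains under either reading.

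The plan does not exclude saline volunteers from the ANOVA, and their changes could be shown beside those of R848. That is fair: the text supports saying only that no direct comparison is named. Two separate baseline tests, one per arm, still do not estimate the difference between arms.

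A 4 v 2 comparison is weak, the magnitudes rest on assumed SDs, and nothing was simulated for counts or CRP. All true. The temperature range is wide and its curve is zero at 24 and 48 h. Weakness argues for intervals and descriptive reading, not for omitting the control, and the plan already compares CXCL10 at 4 v 2.

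The random-intercept model also has a limit. If within-person SD doubles at 1 h in the R848 arm only, its 95% interval covers about 94% at 4 v 2 and 86-87% at 4 v 8. A change score at each time is a defensible alternative, with lower power: at 4 v 2 it finds 0.7 L in 58-99% of runs and 0.35 L in 20-58%. For cohorts this small, individual profiles by arm carry much of the information.

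Finally, Appendix B also schedules spirometry and observations at 15 min and Day 8. The figures here apply to the six times of section 7.3.

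**Conclusion.** The concern holds and should be fixed. It rests on the text: the stated test cannot separate an R848 effect from time or procedure effects, no R848-saline comparison is named for these secondary outcomes, the form of the ANOVA and the people analysed are left open, and CRP has no analysis. The CRP gap is a separate, smaller omission.

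The size depends on assumed SDs. A shared time effect can make the baseline test significant far more often than 5% with no drug effect, while the contrast with saline stays near 5%. If run as independent groups, the test would miss most mean FEV1 falls of 0.7 L. These are secondary outcomes in a small dose-finding study, so the consequence is weak or misattributed group-level reporting. It does not show a failure of safety monitoring.

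**What to change.** Replace the ANOVA sentence in section 12.1 with the following.

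- A repeated-measures or mixed model with a random participant intercept, using baseline and the post-challenge times listed in section 7.3, with terms for group, time and group × time. If unequal variance is expected after R848, name a change-score analysis at each time instead.
- The R848-minus-saline difference in change from baseline, with a 95% interval, for each dose and listed time, read descriptively.
- CRP handled in the same way, with the analysis scale stated for CRP and for the counts.
- In the final analysis, saline pooled across the healthy cohorts, with the asthma saline volunteers kept separate.
- Individual profiles listed by arm.
- A statement of who enters each analysis, and of whether 24 h spirometry and observations precede sputum induction.

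The cost is wording and a little programming; the measurements are already planned. The limits should be disclosed. Single-cohort contrasts, and the asthma contrast throughout, stay at 4 v 2 with the half-widths shown above. Pooled saline reaches 8 only if all four healthy cohorts run, and pooling assumes no drift between cohorts. With five cohorts there are 29 × 5 = 145 intervals, so none should be treated as a confirmatory test.

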11. SAFETY REPORTING DEFINITIONS

11.1 *Adverse Event (AE)*

An AE or adverse experience is any untoward medical occurrence in a participant, which does not necessarily have a causal relationship with the intervention. An AE can therefore be any unfavourable and unintended sign (including an abnormal laboratory finding), symptom or disease temporally associated with the study, whether or not considered related to the study.

11.2 *Serious Adverse Event (SAE)*

A serious adverse event or reaction is any untoward medical occurrence that at any dose:

- Results in death,
- Is life-threatening,

NOTE: The term "life-threatening" in the definition of "serious" refers to an event in which the participant was at risk of death at the time of the event; it does not refer to an event which hypothetically might have caused death if it were more severe, including an event which:

- Requires inpatient hospitalisation or prolongation of existing hospitalisation,
- Results in persistent or significant disability/incapacity, or
- Is a congenital anomaly/birth defect.
- Other important medical events*

*Other events that may not result in death, are not life threatening, or do not require hospitalisation, may be considered a serious adverse event when, based upon appropriate medical judgement, the event may jeopardise the patient and may require medical or surgical intervention to prevent one of the outcomes listed above.

Planned admission to hospital for a pre-existing condition will not be considered an SAE.

11.3 *Expected Adverse Events and Serious Adverse Events Exempt from Recording*

Nasal R848 challenge administered at doses between 10 - 100 µg/mL in healthy participants and those with asthma has previously been well tolerated with no reported SAEs (11, 12).

R848 is a synthetic substance that when given to in the respiratory tract is designed to mimic the effects of a viral infection such as influenza. Therefore, expected AEs that participants may experience include transient flu-like symptoms such as:

- Cough
- Runny nose
- Mild headache
- Low grade fever
- Lethargy
- Myalgia

If a high-grade fever occurs that is more sustained or causes symptoms, then volunteers will be offered an antipyretic such as paracetamol.

Participants with asthma will be carefully monitored after R848 dosing. If their FEV1 drops by >20% then they will be administered nebulised salbutamol as a bronchodilator.

Nasal sampling using nasosorption and nasal cytology brush may cause:

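### The only planned FEV1 tolerability analysis tests a mean change from baseline, which does not respond to a severe fall in one volunteer; no per-participant summary is planned

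*Combined protocol and SAP*

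**What the plan says.** Section 6.2 sets secondary objective (i): "To assess clinical tolerability of inhaled R848 with regards to FEV₁". Section 7.3(i) defines the outcome as change in FEV1 "after 1, 4, 8, 24 and 48 hours of single ascending dose inhaled R848". Section 12.1 gives the only analysis: FEV1, together with temperature, pulse, blood pressure and leukocyte counts, "measured after challenge will be compared to baseline values using one-way analysis of variance (ANOVA". Section 12.3 adds: "A P-value of < 0.05 will be taken to indicate statistical significance". The plan does not say whether the ANOVA is a repeated-measures model, or whether it is run per arm, per cohort or pooled.

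The cohort structure is in section 7.1: "For each dose-cohort (n = 6), participants will be randomised to either R848 (n = 4) or saline (n = 2".

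A fall in one person's FEV1 appears only as a trigger for treatment. Section 10.2 has bronchodilators on standby for volunteers with "symptoms of breathlessness or tight chest associated with a significant drop" in FEV1, put at 20% or more. Section 11.3 says of participants with asthma: "If their FEV1 drops by >20% then they will be administered nebulised salbutamol as a bronchodilator". Section 11.5 has all adverse events recorded with severity and relatedness. Section 12 contains no count of individual falls, no largest fall per person and no tabulation of adverse events.

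**The concern.** Tolerability of an inhaled challenge is a matter of what happens to each person. The protocol recognises this clinically, since it acts on a fall of about 20% in one volunteer. The analysis asks something else: whether the average across volunteers has moved from baseline by more than the noise. One large fall moves the average, but it also inflates the error term against which the average is judged.

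At stake is the reported result for secondary objective (i), and the support it gives to the synopsis aim of finding a clinically tolerable dose. A statement that FEV1 did not change significantly could be written about a dose at which one of four people had a marked fall, and the plan commits to no other FEV1 result that would show it.

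**Working it through.** The plan states no power, SD or detectable change for FEV1, so there is no figure to reproduce.

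**Inputs from the documents.** Four R848 participants per cohort (7.1); baseline plus 1, 4, 8, 24 and 48 hours, so k = 6 times (7.3); significance at 0.05 (12.3). I take the ANOVA as run on the four R848 participants of one cohort, because the plan does not specify.

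**Assumed, not in the documents.** Within-person SD of 2, 3 or 5 points (percent of baseline); between-person SD of 12 points; a fall that peaks at 1 h, is half as large at 4 h and has gone by 8 h.

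**Step 1: exact result without noise.** Let m of n people share the same fall and the rest not change. Let S be the sum of squared deviations of one faller's six values about that person's own mean.

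- Time sum of squares: n × (m/n)² × S = m²S/n.
- Total within-person sum of squares: mS.
- Error sum of squares: mS − m²S/n = m(n − m)S/n.
- F = [m²S/n ÷ (k − 1)] ÷ [m(n − m)S/n ÷ ((k − 1)(n − 1))] = m(n − 1)/(n − m).

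S cancels, so neither the depth nor the time course of the fall matters. With n = 4 and df 5 and 15:

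| Fallers of 4 | F | P |
|---|---|---|
| 1 | 1×3/3 = 1.00 | 0.45 |
| 2 | 2×3/2 = 3.00 | 0.045 |
| 3 | 3×3/1 = 9.00 | 0.0004 |

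For one faller, F = 1×(n − 1)/(n − 1) = 1 at every n. P is 0.44 at n = 6 and 0.42 at n = 16 or 20. Pooling cohorts or enlarging them would not change this.

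**Step 2: with noise.** Simulated chance that P < 0.05 with one faller of four, repeated-measures form:

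| Within-person SD | 20% fall | 30% fall | 40% fall |
|---|---|---|---|
| 2 | 0.3% | <0.1% | <0.1% |
| 3 | about 1.8% | 0.3% | <0.1% |
| 5 | 3.8% | 2.2% | about 1% |

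Every entry is below the 5% expected when nobody falls, and each row drops as the fall gets worse. The literal unpaired ANOVA on absolute values flags one faller in about 0.1% or less.

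**Step 3: more than one faller.** Over the same SDs and falls of 20% to 40%:

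| Fallers of 4 | Repeated measures | Unpaired |
|---|---|---|
| 2 | about 22–52% | about 1–6% |
| 3 or 4 | about 80% or more | about 40% even when all four fall by 20% |

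**Step 4: what a count would show.** One faller of four is reported as 1/4 (exact 95% CI 0.6% to 80.6%). For zero events the exact upper limit is 1 − 0.025^(1/n). This gives 60% for 0/4 and 21% for 0/16, where 16 = 4 doses × 4 healthy R848 participants if all four cohorts are run.

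**The case against.** The strongest reply is that individual safety does not depend on section 12. Spirometry is monitored after challenge, a fall of about 20% prompts treatment, every adverse event is recorded with severity, and escalation has its own condition that the dose be tolerable. The ANOVA can then be seen as a description of an exploratory secondary outcome. Much of this stands, and it rules out several stronger readings that a reader might infer:

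- **That a severe fall would go unnoticed.** Sections 10.2, 11.3 and 11.5 point the other way. It would be seen at the bedside and could be recorded as an adverse event.
- **That the ANOVA decides escalation.** Section 10.2 does not link the two, and nothing says that a non-significant P will be read as tolerable.
- **That one fall of 20% makes a dose intolerable.** The documents use that level to trigger treatment, not as an endpoint or a dose-limiting definition.
- **That four per cohort is the cause.** Step 1 shows the same F at any n.
- **That two or three fallers would normally be missed as well.** A paired t-test on four changes gives P = 0.18 and 0.058 for two and three equal fallers, but that is not the planned test. The repeated-measures form gives 0.045 and 0.0004 without noise, and detects three or four fallers well. Poor detection beyond two fallers arises only under the unpaired form, which would be a separate fault of model choice.

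What the reply does not answer is that recording events is not an analysis. Section 12 plans nothing with them, and the tolerability condition in 10.2 is not defined. The one written FEV1 analysis is still the one that does not respond to a single large fall.

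**Conclusion.** The point holds in this form: the planned FEV1 analysis is a test of a mean, and it does not respond to a severe fall in one volunteer. The noise-free result (F = 1.00; P = 0.45 at n = 4) needs no assumption about SD. The figure of at most about 4%, and about 0.1% or less for the unpaired form, rests on the assumed within-person SD of 2 to 5 points, between-person SD of 12 points, falls of 20% to 40%, and the reading that the test is run on four R848 participants. Two of four falling is an intermediate case; three or four falling is detected if the model is repeated-measures. The consequence is for what is reported about tolerability, not for whether an event is noticed or treated. It should be changed, because the stated method does not address the objective it serves and a better summary needs no new data.

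**What to change.** In sections 7.3(i) and 12.1:

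1. Report for each participant the largest percentage fall in FEV1 from the 0 h value over the post-challenge readings, listed by dose and arm. State which scheduled readings count, use observed values only (the own-mean imputation in 12.4 could shrink a fall), and mark readings taken after a bronchodilator.
2. Report the number of participants whose fall reaches the 20% level the protocol already uses, for R848 and saline, per dose and over all healthy R848 doses, with exact 95% confidence intervals. This is a descriptive summary only. Sections 10.2 and 11.3 must first be reconciled: one has 20% or more with symptoms, the other more than 20% in participants with asthma without mention of symptoms.
3. Keep the mean profiles as description, and state that a non-significant mean change is not evidence of tolerability.

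The cost is a change of wording and slightly more reporting, with no new visit, reading or participant. The stated certainty about tolerability becomes less favourable, since even no events in a cohort leaves an upper limit of 60%.

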9.1.5 Spirometry

Volunteers will perform spirometry at the screening visit and throughout the study period.

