9.3 Screening and Eligibility Assessment

Participants in this study will be recruited from Cambridge University Hospitals (CUH), Royal Papworth Hospital (RPH), Heart and Lung Research Institute (HLRI), University of Cambridge, volunteer databases, local advertising in the Cambridge area and wider East of England region, as well through online platforms. Participants from CUH may be recruited from outpatients (in particular, departments of allergy and asthma) or comprise of staff working there. Employees or students at the University of Cambridge who express an interest in taking part are also eligible. Advertisements for the study will be through organisational posters, newsletters, online bulletins, local newspapers, online platforms, and social media channels.

Pre-screening of interested participants will primarily involve interaction with a dedicated study website (www.lungchallenge.org.uk) or by email and telephone screening. They will be able to download the Participant Information Sheet (PIS) from the study website.

An online pre-screening questionnaire hosted using REDCap software will be utilised to ascertain basic eligibility for the study in an anonymised form. If participants are not eligible no data will be stored. If participants may be eligible, they will be asked for further demographic and medical details to help ascertain eligibility and their data will be stored using the University of Cambridge's Secure Data Hosting Service which has a Safe Haven for Personal Identifiable Data <https://cscs.medschl.cam.ac.uk/server-services/secure-data-hosting-service/>.

Subsequently, for potentially eligible participants, a screening visit will be undertaken at the Cambridge Clinical Research Centre (CCRC) to evaluate the following:

Demographics: date of birth, gender, race, smoking status.

Medical History: Details of any history of disease or surgical interventions and systems review to determine inclusion/exclusion criteria.

Concomitant Medication: All over the counter or prescription medication, vitamins, and/or herbal supplements will be recorded.

Physical Examination as well as physiological observations, height, weight, and temperature will be recorded.

ECG Test: A 12-lead ECG will be undertaken for each participant.

Laboratory Tests: Biochemistry, full blood count, liver function test, total IgE, PBMC isolation, skin prick allergy testing, and a pregnancy test (for women) will be performed.

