9.4.2 Visit 2 (Day 2)

This will take place at 48 hours to monitor physiological observations, spirometry and perform blood tests.

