9.4.3 Visit 3 (Day 8)

This will take place at 7 days after challenge to monitor physiological observations, spirometry and perform blood tests. This will then be the end of the study for participating volunteers.

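### Section 12.4 fills a missing clinical value with the volunteer's own mean whatever the time point, which biases change at fixed hours unless the missing value equals that mean

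*Combined protocol and SAP*

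**What the plan says.** Section 12.4 of the combined protocol and SAP reads, in full: "Missing clinical data points will be imputed as the mean of values from that volunteer". It does not restrict which of the volunteer's readings enter the mean, makes no exception for a missing baseline, and does not define which variables are clinical. No other missing-data method or sensitivity analysis appears.

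Section 7.3 defines FEV1 and the physiological observations as changes "after 1, 4, 8, 24 and 48 hours of single ascending dose inhaled R848". Eosinophil and lymphocyte counts and CRP are changes at 4, 24 and 48 hours. Section 12.1 says that FEV1, observations and leukocyte counts "measured after challenge will be compared to baseline values using one-way analysis of variance (ANOVA"; it does not say whether this is done by dose cohort or pooled, or as repeated measures.

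Readings exist outside the outcome times. Section 9.1.5 says "Volunteers will perform spirometry at the screening visit and throughout the study period". Appendix B schedules spirometry and observations at 15 min as well, and section 9.4.3 adds a Day 8 visit: "This will take place at 7 days after challenge to monitor physiological observations, spirometry and perform blood tests". Screening bloods under section 9.3 include "Biochemistry, full blood count, liver function test, total IgE".

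**The concern.** A volunteer's average over several days does not estimate the value at a particular hour after a single dose. If the challenge has an effect that changes over time, the rule pulls the missing value toward the volunteer's overall level. It hides part of an effect when the missing time is the worst one and adds an effect when the missing time falls after recovery.

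FEV1 and the observations are the trial's tolerability outcomes, and groups are small: four active and two saline per dose cohort. Because 12.4 does not say which readings count, two analysts could also fill the same gap with different numbers.

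**Working it through.** **No stated figure to reproduce.** The plan gives no missing-data rate, response curve or SD. What follows from the rule itself is the formula; the profiles are assumptions.

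**Formula.** For a missing time t after baseline:

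bias in change at t = mean of the volunteer's other values - true value at t.

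For a missing 0 h value, the same error enters the baseline and is subtracted from every change.

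**Main example.** Assumed FEV1 of 4.0, 3.2, 3.4, 3.6, 4.0 and 4.0 L at 0, 1, 4, 8, 24 and 48 h (sum 22.2 L), with the mean taken over these six times only.

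| Missing | Filled value | Change shown | True change |
|---|---|---|---|
| 1 h | (22.2 - 3.2)/5 = 3.80 L | -5% | -20% |
| 48 h | (22.2 - 4.0)/5 = 3.64 L | -9% | 0% |
| 0 h | (22.2 - 4.0)/5 = 3.64 L | 1 h: 3.2/3.64 = -12.1% | -20% |
| 0 h | 3.64 L | 24 h and 48 h: 4.0/3.64 = +9.9% | 0% |

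**Which readings enter the mean.** Two other readings of the rule give:

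- Post-challenge outcome times only: missing 1 h = 15.0/4 = 3.75 L (-6.25%); missing 48 h = 14.2/4 = 3.55 L (-11.25%).
- All scheduled readings, with screening and Day 8 assumed 4.0 L and 15 min assumed between 3.2 and 4.0 L: missing 1 h = 3.775 to 3.875 L (-5.6% to -3.1%); missing 48 h = 3.675 to 3.775 L (-8.1% to -5.6%).

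The answer changes with the reading, but the direction does not. Limiting the mean to post-challenge values does not cure the problem.

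**A different curve.** Assumed FEV1 as a percentage of baseline: 100, 95, 80, 90, 95, 100 at the same six times, so the nadir is at 4 h. Missing 4 h = (100 + 95 + 90 + 95 + 100)/5 = 96, a change of -4 (true -20). Missing 48 h = (100 + 95 + 80 + 90 + 95)/5 = 92, a change of -8 (true 0). If the curve is scaled to a nadir of 10% or 30%, missing 4 h shows -2 or -6 (true -10 or -30), and missing 48 h shows -4 or -12 (true 0).

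**Sustained and flat profiles.** If a change D lasts from 1 h to 48 h, one missing post-dose value is filled as (0 + 4D)/5 = 0.80D over the six times. If the profile is flat, the bias is zero.

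**Group level.** Suppose four active volunteers share the main profile and one value is filled. The mean change at 1 h is (3 × -20 - 5)/4 = -16.25% (true -20%); at 48 h it is (3 × 0 - 9)/4 = -2.25% (true 0%). If the 16 active volunteers without asthma were pooled on this same profile, the figures would be (15 × -20 - 5)/16 = -19.1% and -9/16 = -0.6%.

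**Spread.** The effect on the reported spread has no fixed direction.

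- No response, independent noise of equal variance: a filled change has variance 4/25 + 16/25 = 0.8 in units of the within-person variance, against 2 for a real change. The SD ratio is sqrt(0.8/2) = 0.63, so the spread is too small.
- Transient response, as in the group of four above: changes of -20, -20, -20 and -5 have SD 7.5 points where the true SD is 0; at 48 h, changes of 0, 0, 0 and -9 have SD 4.5 points. The spread is too large.

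**The case against.** Several objections limit the point, and most of them stand.

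- **Transience.** Section 11.3 says "expected AEs that participants may experience include transient flu-like symptoms such as" and lists cough, runny nose, headache, low-grade fever, lethargy and myalgia. Only temperature among the secondary outcomes is close to this. A reader might infer that the protocol expects FEV1 or cell counts to fall and recover; it does not say so. The 20% fall used above has the size of the bronchodilator threshold in sections 10.2 and 11.3, which is not an expected response. At low doses the profile may be flat.
- **Variability.** It is tempting to say that single imputation always makes the data look less variable. The calculation above shows that this fails under a transient response, so no general claim can be made.
- **Scope.** Clinical data points clearly include FEV1 and the observations. Whether they include blood counts, CRP or CXCL10 is not stated, so damage to the primary outcome cannot be claimed. If sputum CXCL10 were covered, its only other scheduled value is screening (section 9.1.4), and a missing 24 h result would become a change of exactly zero.
- **Weight of one value.** One filled value is a quarter of the active group only if the ANOVA is run by dose cohort. Section 12.1 gives the four-against-two comparison for CXCL10 only.
- **Exposure.** Volunteers stay in the unit until 24 h and staff take the measurements, so gaps in that period, including 0 h, should be rare. Section 9.4.2 says of Visit 2: "This will take place at 48 hours to monitor physiological observations, spirometry and perform blood tests". That this return visit is the likelier gap is an assumption.
- **Escalation.** A reader might infer that imputed values decide the next dose. Section 10.2 makes escalation depend on CXCL10 and tolerability but does not say that imputed values are used.

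None of this defends the rule itself. Whenever a value is missing and the profile is not flat, the rule generally gives a wrong change at that hour, and nothing in the documents offers a reason for using it.

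**Conclusion.** The rule in 12.4 does not fit outcomes defined as change at fixed hours. That the bias exists, and its direction for a given profile, follow from the rule, so confidence in both is high. Confidence in its size is not high: the figures of -5% for -20% and -9% for 0% rest on an assumed profile and on averaging over the six outcome times. With no missing values or a flat profile the bias is about zero.

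The finding concerns secondary outcomes, certainly FEV1 and the observations. It does not establish an effect on CXCL10 or on dose escalation. It should be fixed, at the lower end of that grade, because the realised effect may be small while the correction is simple.

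**What to change.** In section 12.4:

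- Delete the mean-imputation rule and analyse observed values only, stating that this applies to CXCL10 as well.
- Where the 0 h value is missing, leave that volunteer out of the change-from-baseline comparison for that variable.
- Report the number of missing values and the reasons by dose, arm and time.

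In section 12.1, if the ANOVA is meant as repeated measures, use a form that keeps volunteers with incomplete data, for example a mixed model with time as a factor. Otherwise state that incomplete volunteers drop out of that test.

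**Cost.** One paragraph in 12.4 and possibly one sentence in 12.1. There will be slightly fewer data points. In a classical repeated-measures ANOVA by dose cohort, one gap would take the active group from four to three. Leaving out a volunteer without a 0 h value has the same cost. Screening spirometry could serve as a substitute baseline, but only under a rule written in advance; leaving the volunteer out is simpler. Observed-only results are unbiased only if missingness is unrelated to the response, which is why the counts and reasons must be shown.
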